6.2.4. Handling of other missing data

6.2.4.1. Immunogenicity data

Missing immunogenicity data are not imputed.

6.2.4.2. Daily recording of solicited AEs

When a specific solicited AE is marked as having not occurred following a specific vaccination (i.e. SDTM CE.CEOCCUR=N for the specified post-vaccination period for the solicited AE in question), all daily measurements will be imputed as Grade 0.

When a specific solicited AE is marked as having occurred following a specific vaccination (i.e. SDTM CE.CEOCCUR=Y for the specified post-vaccination period for the solicited AE in question), any missing daily recordings will be given an imputed value which allows them to contribute to the 'Any' rows but not to specific grade rows of the solicited AE summary tables.

When the occurrence of a specific solicited AE is not present (i.e. SDTM CE.CEOCCUR is neither Y nor N for the specified post-vaccination period for the solicited AE in question) all missing daily recordings will be given an imputed value which allows them to contribute to the 'Any' rows but not to specific grade rows of the solicited AE summary tables.

The following table shows how solicited events are coded for intensity.

Table 6 Intensity scales for solicited AEs – Attribution for codes for Diarrhea, Vomiting and Fever

Event	Infant		
	Intensity grade (Collected or measured)	Intensity grade (code attributed)	Parameter
Loss of appetite	0	0	Appetite as usual
	1	1	Eating less than usual/no effect on normal activity
	2	2	Eating less than usual/interferes with normal activity
	3	3	Not eating at all
Irritability/Fussiness	0	0	Behavior as usual
	1	1	Crying more than usual/no effect on normal activity
	2	2	Crying more than usual/interferes with normal activity
	3	3	Crying that cannot be comforted/prevents normal activity
Cough/runny nose	0	0	Normal
	1	1	Cough/runny nose which is easily tolerated
	2	2	Cough/runny nose which interferes with daily activity
	3	3	Cough/runny nose which prevents daily activity
Diarrhea	looser than normal stools/day	0	Normal (0-2 looser than normal stools/day)
		1	3 looser than normal stools/day
		2	4-5 looser than normal stools/day
		3	≥ 6 looser than normal stools/day
Vomiting	episodes of vomiting/day	0	Normal (no emesis)
		1	1 episode of vomiting/day
		2	2 episodes of vomiting/day
		3	≥3 episodes of vomiting/day
Fever ⁺	Axillary Temperature (°C)	0	Normal (< 37.5°C)
		1	37.5°C – < 38.0°C
		2	38.0°C – < 39.5°C
		3	≥ 39.5°C
		4	≥ 39.5°C, lasts more than 5 consecutive days

^{*}Axilla is the preferred route to measure temperature in China. If temperature is collected by other routes, the following conversion will be applied:

- Axillary temperature = oral temperature - 0.2°C
- Axillary temperature = rectal temperature - 0.3°C.

The following table shows how participants contribute to each category for a specific solicited AE over the Day X to Day Y post-vaccination period:

Solicited AE category	Participants included in the calculation of the numerator
Any	All participants with at least 1 occurrence of the solicited AE at grade 1, grade 2, grade 3 or grade 4 between Day X and Day Y or with the solicited AE marked as present and at least 1 missing daily recording between Day X and Day Y
At least grade 1	All participants with at least 1 occurrence of the solicited AE at grade 1, grade 2, grade 3 or grade 4 between Day X and Day Y
At least grade 2	All participants with at least 1 occurrence of the solicited AE at grade 2, grade 3 or grade 4 between Day X and Day Y
At least grade 3	All participants with at least 1 occurrence of the solicited AE at grade 3 or grade 4 between Day X and Day Y

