9.4. Analysis of safety

Safety analysis will be performed on the ES.

Participants who missed reporting events (solicited/unsolicited AEs or concomitant medications) will be treated as participants without the events (solicited/unsolicited AEs or concomitant medications, respectively).

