
 To evaluate the reactogenicity of Rotarix PCV-free and IPV in terms of solicited systemic events. To assess the safety of Rotarix PCV-free in terms of unsolicited AEs and serious adverse events (SAEs) and safety of IPV in terms of SAEs. 	
 Solicited AEs 
 For each solicited systemic event, percentage of participants reporting the occurrence of the event within 14 days (Day 1- Day 14) after Dose 1 and Dose 2 of Rotarix and IPV Unsolicited AEs 
 Percentage of participants reporting the occurrence of unsolicited AEs within 31 days (Day 1- Day 31) after each dose of Rotarix, according to the MedDRA classification. SAEs: 
 Percentage of participants reporting SAEs from the first dose of the study intervention up to study end in the Co-administration and Staggered groups.

Ab: Antibody; GMC: Geometric mean Ab concentration; GMT: Geometric mean Ab titer; IgA: Immunoglobulin A; IPV: Inactivated poliovirus vaccine; MedDRA: Medical Dictionary for Regulatory Activities; mL: milliliter; PCV: *Porcine circovirus*; SAE: Serious Adverse Event; U: Unit

*Seroconversion rate for IPV neutralizing Ab is defined as percentage of participants with

[figure not shown]
- Titer $\geq 1:8$ at 1 month after 3 dose primary schedule of IPV in participants with titer $<1:8$ pre-vaccination
- Titer ≥ 4 -fold increase in titer 1 month after 3 dose primary vaccination schedule in participants with titer $\geq 1:8$ pre-vaccination.

Note: the 4-fold increase will take into consideration the expected decline in maternal antibodies with estimated half-life of 28 days.

**Seroconversion rate for anti-RV IgA Ab is defined as the percentage of participants who were initially seronegative (i.e., with anti-RV IgA Ab concentration <20 U/mL prior the first dose of *Rotarix*) and developed anti-RV IgA Ab concentration ≥ 20 U/mL at 1 month post Dose 2.

** complementary details on estimand including impact of intercurrent events on the analysis is available in Section 3 and Section 4.

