4.1.2. Reactogenicity

Participants without events (solicited/unsolicited AEs or concomitant medications) reported will be treated as participants without the events (solicited/unsolicited AEs or concomitant medications, respectively).

Refer to Section 6.2.4.2 for the intensity grading of solicited AEs.

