4.8. Changes to Protocol Defined Analyses

There were no changes or deviations to the originally planned statistical analysis specified in the protocol amendment 1 (Dated: 25 October 2023).

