6.2.8. Counting rules for occurrences of solicited adverse events

When the occurrences of solicited adverse events are summarized, each event recorded as having occurred during a specific period will be counted as only 1 occurrence regardless of the number of days on which it occurs.

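### SAP 6.2.4.2 gives conflicting rules on whether a solicited event with a blank occurrence flag, a missing diary day and no graded day counts in the Any row

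*SAP*

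**What the plan says.** SAP 6.2.4.2 (Daily recording of solicited AEs) sets three rules, according to the occurrence flag for a given symptom after a given vaccination.

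- **Flag N:** every day is set to grade 0.
- **Flag Y:** missing days count towards the *Any* row but not towards any specific grade row.
- **Flag neither Y nor N:** "all missing daily recordings will be given an imputed value which allows them to contribute to the" *Any* rows, again without entering a specific grade row.

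The category table later in the same section defines who enters each numerator. A participant has two routes into *Any*. The first is a day graded 1 to 4. The second is to be a participant "with the solicited AE marked as present and at least 1 missing daily recording between Day X and Day Y". The *At least grade 1* row keeps only the first route: "All participants with at least 1 occurrence of the solicited AE at grade 1, grade 2, grade 3 or grade 4" in the period.

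Two general rules bear on participants with nothing reported. SAP 4.1.2 says: "Participants without events (solicited/unsolicited AEs or concomitant medications) reported will be treated as participants without the events". Protocol 9.4 says: "Participants who missed reporting events (solicited/unsolicited AEs or concomitant medications) will be treated as participants without the events". SAP 4.8 adds: "There were no changes or deviations to the originally planned statistical analysis specified in the protocol amendment 1".

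The output concerned is a descriptive secondary endpoint (SAP 1.1): "For each solicited systemic event, percentage of participants reporting the occurrence of the event within 14 days" of vaccination. SAP 4.5 tabulates it with exact 95% confidence intervals.

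**The concern.** A blank flag is not a flag of presence, and the imputed value is kept out of the grade rows. A participant with a blank flag, a missing day and no graded day therefore meets neither route in the table, yet the third paragraph places that participant in *Any*. One missing day out of 14 is enough: read literally, 13 days at grade 0 and one blank day become an occurrence.

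Two programmers could each follow the SAP and produce different percentages. Under the paragraph, the *Any* row would include infants for whom nobody recorded the symptom, although the endpoint is about reported occurrence. Where the flag and all 14 days are blank, the paragraph gives the reverse of Protocol 9.4, while SAP 4.8 declares no departure from the protocol.

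**Working it through.** **Step 1. Do the two rules differ, and where?** The documents state no figure for this point, so there is none to reproduce. Both rules were applied to each flag value crossed with five 14-day diary patterns. Each cell shows *paragraphs 1–3 / category table*, where *in* means counted in *Any*.

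| Diary pattern | Flag Y | Flag N | Flag blank |
|---|---|---|---|
| All days grade 0 | out / out | out / out | out / out |
| 13 days grade 0, 1 missing | in / in | out / out | **in / out** |
| All 14 days missing | in / in | out / out | **in / out** |
| 1 day grade 1, 12 days grade 0, 1 missing | in / in | out / out | in / in |
| 1 day grade 1, 13 days grade 0 | in / in | out / out | in / in |

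Of the 15 combinations, the rules disagree in exactly two. Both have a blank flag, at least one missing day and no graded day.

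**Step 2. Size.** Inputs:

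- n = 200 per group (SAP section 5), assuming all are in the Exposed Set.
- g = participants counted under the table. Assumed: 20 or 4.
- b = further participants with a blank flag, at least one missing day and no graded day, for the same symptom and dose. Assumed: 2, 4 or 10, which is 1%, 2% or 5% of 200.

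The documents give neither g nor b.

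Formulas:

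- Table rule: g/n.
- Third paragraph: (g + b)/n.
- Difference: b/n, so one participant is 1/200 = 0.5 percentage point.
- Exact (Clopper-Pearson) 95% CI for x out of n: lower limit is the 2.5% quantile of Beta(x, n − x + 1); upper limit is the 97.5% quantile of Beta(x + 1, n − x).

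| b | g = 20 | g = 4 |
|---|---|---|
| Table rule (any b) | 20/200 = 10.0% (6.2–15.0) | 4/200 = 2.0% (0.5–5.0) |
| Paragraph, b = 2 | 22/200 = 11.0% (7.0–16.2) | 6/200 = 3.0% (1.1–6.4) |
| Paragraph, b = 4 | 24/200 = 12.0% (7.8–17.3) | 8/200 = 4.0% (1.7–7.7) |
| Paragraph, b = 10 | 30/200 = 15.0% (10.4–20.7) | 14/200 = 7.0% (3.9–11.5) |

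The absolute shift does not depend on g, but the relative shift does. With b = 4, the percentage rises by a factor of 12.0/10.0 = 1.2 for the commoner symptom and 4.0/2.0 = 2 for the rarer one. The difference b/n needs no assumption about why flags are blank.

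**Step 3. A check the analysis could carry.** The *At least grade 1* row is free of this imputation. *Any* minus *At least grade 1* is therefore an upper bound on the effect. It is only a bound because it also contains flag Y participants with missing days and no graded day.

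**The case against.** The strongest reply is that the third paragraph works at the level of a day and never mentions a numerator, while the table is the only rule in the section that says which participants are counted. On that reading the paragraph is loose coding language and the table governs. This does not hold. The flag Y paragraph uses the same language about contributing to *Any*, and there the table does count the participant. Nor can a blank flag be stretched to mean presence, because the third paragraph itself sets it apart from an event marked as having occurred.

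A second reply is that a specific missing-data rule may refine a general one, and that counting unknowns as events could be a deliberate, cautious safety choice. The documents do not settle intent. If it was deliberate, however, the table was left unaligned and the departure from Protocol 9.4 was not declared in SAP 4.8.

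Several points stand:

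- The contradiction rests on the paragraph against the table. SAP 4.1.2 and Protocol 9.4 are the real outside support, and both are general. The endpoint wording adds little. So does SAP 6.2.8 ("each event recorded as having occurred during a specific period will be counted as only 1 occurrence"), which is chiefly a rule against counting repeated days.
- The documents do not say how the flag is collected or derived, so a blank flag beside 13 recorded grade 0 days may be rare or may never arise. Protocol 10.3.6.1 also requires returned cards to be verified and missing ones pursued, which should keep blanks few. The 5% scenario is best read as a high one.
- SAP 4.5 does not list *At least grade 1* among its planned summaries, although the table defines it. The bound in Step 3 is available only if that row is produced.

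**Conclusion.** The concern holds, as a minor internal inconsistency. For a blank flag with a missing day and no graded day, the SAP gives two incompatible answers for the *Any* numerator and no order of precedence. The other relevant rules favour the table.

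The effect is 0.5 percentage point per affected participant in a group of 200, for a given symptom and dose, and it is proportionally largest for rare symptoms. The total depends on a blank-flag rate that the documents do not give, so the 1, 2 and 5 point shifts are illustrations.

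Confidence is high that the texts conflict. Whether the conflict changes any reported figure depends on how many blank flags occur. Only descriptive solicited-event percentages can move. No grade row, SAE table or hypothesis test depends on it.

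**What to change.** Rewrite the third paragraph of SAP 6.2.4.2 to agree with the category table: where the flag is neither Y nor N and no day is graded 1 or higher, the participant does not enter the *Any* numerator. Deleting the paragraph would also remove the conflict, but rewriting is better because it leaves an explicit rule for the blank flag. Keep the flag Y rule as it is.

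Optionally, add the number of blank flags by group, dose and symptom to the compliance table in SAP 6.1.6, so that a reader can see how often the rule was used. This is not needed to resolve the conflict.

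The cost is one SAP paragraph, with no protocol change and no new data. The optional columns use data already collected.

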6.2.4.3. Unsolicited adverse events

Unsolicited AE summaries will include unsolicited AEs and SAEs. Solicited events collected within the Day 1 -14 assessment period will be reported in the clinical event (CE) domain while unsolicited events will be reported in the AE domain. Following CBER's request to comply with the CDISC Vaccines Therapeutic Area Guide, solicited events that continue beyond the assessment period will also be reported in the AE domain. These solicited events will not be included in the summaries of unsolicited AEs but will be reported separately.

Missing severity, relationship with study vaccine, and outcome of unsolicited adverse events will not be replaced and will appear as 'UNKNOWN' in all statistical output.

6.2.5. Age at vaccination in weeks

Age at vaccination will be displayed in weeks. It will be calculated as the number of complete weeks between the date of birth (DOB) and the date of vaccination. For example:

DOB = 10JUN2019, Date of vaccination = 28JUL2019 -> Age = 6 weeks

DOB = 10JUN2019, Date of vaccination = 29JUL2019 -> Age = 7 weeks

Incomplete birthdate will follow the general imputation for incomplete date (refer to Section [6.2.3](#)).

6.2.6. Onset day

The onset day for an event (e.g., AE, medication, vaccination) is the number of days between the last study vaccination and the start date of the event. This is 1 for an event occurring on the same day as a vaccination (and reported as starting after vaccination).

6.2.7. Counting rules for combining solicited and unsolicited adverse events

For output combining solicited and unsolicited adverse events, all serious adverse events will be considered general events since the administration site flag is not included in the expedited adverse event case report form (CRF) pages.

Multiple events with the same preferred term which start on the same day are counted as only 1 occurrence.

6.2.8. Counting rules for occurrences of solicited adverse events

When the occurrences of solicited adverse events are summarized, each event recorded as having occurred during a specific period will be counted as only 1 occurrence regardless of the number of days on which it occurs.

6.2.9. Immunogenicity data

- In general, the assay cut-off is the value under which there is no quantifiable result available. For an assay with a specific ‘assay cut_off’, the numerical immunogenicity result is derived from a character field (IS.ISSTRES):
 - if ISSTRES is ‘NEG’ or ‘-’ or ‘(-)’, numeric result= assay cut_off/2,
 - if ISSTRES is ‘POS’ or ‘+’ or ‘(+)’, numeric result = assay cut_off,
 - if ISSTRES is ‘< value’ and value<=assay cut_off, numeric result =assay cut_off/2,
 - if ISSTRES is ‘< value’ and value>assay cut_off, numeric result =value,
 - if ISSTRES is ‘> value’ and value<assay cut_off, numeric result =assay cut_off/2,
 - if ISSTRES is ‘> value’ and value>=assay cut_off, numeric result =value,
 - if ISSTRES is ‘<= value’ or ‘>= value’ and value<assay cut_off, numeric result =assay cut_off/2,
 - if ISSTRES is ‘<= value’ or ‘>= value’ and value>=assay cut_off, numeric result =value,
 - if ISSTRES is a value < assay cut_off, numeric result = assay cut_off/2,
 - if ISSTRES is a value >= assay cut_off, numeric result = ISSTRES
 - else numeric result is left blank.

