4. STATISTICAL ANALYSES

4.1. General Considerations

4.1.1. Immunogenicity

- GMC/GMT concentrations/titers below the assay cut-off will be given an arbitrary value of half the assay cut-off for the purpose of GMC/GMT calculation.
- The GMC/GMT calculations will be performed by taking the anti-log of the mean of the log concentration/titer transformations.
- Seroconversion rate for IPV neutralizing Ab is defined as percentage of participants with
 - Titer $\geq 1:8$ at 1 month after 3 dose primary schedule of IPV in participants who are seronegative before Dose 1 (titer $< 1:8$ pre-vaccination).
 - ≥ 4 -fold increase in titer 1 month after 3 dose primary vaccination schedule in participants who are seropositive before Dose 1 (titer $\geq 1:8$ pre-vaccination) after adjusting for maternal antibody decay assuming a half-life of 28 days.
- Seroconversion rate for *Rotarix* is defined as the percentage of participants who were initially seronegative (i.e., prior the first dose of *Rotarix*) and developed anti-RV IgA Ab concentration ≥ 20 U/mL 1 month post Dose 2.
- For a given participant and a given immunogenicity measurement time point, missing or non-evaluable measurements will not be replaced.

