4.3.1. Within groups assessment

The following calculations will be performed:

For each group, 1 month post Dose 2 for *Rotarix* PCV-free and 1 month post Dose 3 for IPV timepoint,

- Seropositivity (before Dose 1 and 1 month post Dose 2) and Seroconversion rates for *Rotarix* PCV-free (1 month post Dose 2) and their exact 95% confidence interval (CI) will be computed using the method of Clopper and Pearson [[Clopper](#), 1934],
- GMCs/GMTs were applicable and their exact 95% CIs will be computed.
- The percentage of participants with anti-poliovirus 1, 2, and 3 neutralizing Ab titers $\geq 1:8$ and $\geq 1:64$ and their exact 95% CI for each group at 1 month post Dose 3 will be computed.
- The percentage of participants with anti-RV IgA antibody concentrations ≥ 90 U/mL and their exact 95% CI for each group at 1 month post Dose 2 will be computed.
- The distribution of anti-RV IgA Ab concentrations 1 month post Dose 2 and anti-poliovirus titers 1 month post Dose 3 will be displayed using reverse cumulative curves for the PPS

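### SAP 6.2.9 replaces a result known only to lie below a bound above the assay cut-off with the bound itself, so a possibly negative sample is scored positive

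*SAP*

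**What the plan says.** SAP 6.2.9 converts the laboratory's character result to a number. It explains that "the assay cut-off is the value under which there is no quantifiable result available". A `< value` result has two rows. If the bound is at or below the cut-off, the rule is "and value<=assay cut_off, numeric result =assay cut_off/2", a negative. If it is above, the rule is "and value>assay cut_off, numeric result =value". A separate row gives `<= value`, at or above the cut-off, the value itself.

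The endpoints use these numbers. SAP 4.1.1 counts polio seroconversion as a titer of at least 1:8 "at 1 month after 3 dose primary schedule of IPV in participants who are seronegative before Dose 1"; for other infants it requires a 4-fold rise "after adjusting for maternal antibody decay assuming a half-life of 28 days". RV IgA seroconversion requires an initially seronegative infant to reach 20 U/mL. Secondary endpoints use 1:64 for polio and 90 U/mL for RV IgA (SAP 4.3.1). Code 2020 in SAP 6.1.3 removes from the Per Protocol Set (PPS) an infant whose baseline RV IgA is 20 U/mL or more, or unknown.

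On absent data, SAP 6.2.4.1 states "Missing immunogenicity data are not imputed" and SAP 4.1.1 states that "missing or non-evaluable measurements will not be replaced". Neither defines non-evaluable. Protocol 8.1.4 sets the lowest polio dilution tested at 1:8.

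**The concern.** A `<` result excludes its own bound, yet the rule records the bound as if it had been measured. The less a result tells us, the higher the number it receives: polio `<8` becomes 4, while `<64` becomes 64. Nothing elsewhere in the SAP treats such a result as undecided for a responder endpoint.

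After vaccination the error can only add responders. At baseline it can label a seronegative infant seropositive. For GMT and GMC it enters the top of the possible range. The primary endpoint has little room for false responders: at the planned polio 2 rate, few infants per group are expected not to seroconvert.

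**Working it through.** **Inputs.** Margin -10 points, two-sided 95% Miettinen-Nurminen interval (SAP 2 and 4.2.2); 160 evaluable per group; rates 96.23%, 93.83% and 97.60% (SAP 5); half-life 28 days (SAP 4.2.1); optimal visit intervals (SAP 6.2.2). SAP 6.2.9 gives no numerical cut-offs, so I take 8 for polio and 20 U/mL for RV IgA from the stated thresholds (assumption).

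**Plan's own figure.** Exact binomial enumeration of the score test gives power of 98.6%, 93.8% and 99.8%, against the stated 98.2%, 92.5% and 99.7%. The stated type II errors give 1 - (0.018 + 0.075 + 0.003) = 90.4%, as printed; mine give 92.1%. All agree within 2 points, so the method is fit for the checks below. The coding rule does not affect the sample size.

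**Rule applied literally.**

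| Result | Coded | Scored as | What is known |
|---|---|---|---|
| polio `<8` | 4 | negative | negative |
| polio `<16` | 16 | seropositive; seroconverted if baseline negative | may be below 8 |
| polio `<64` | 64 | the same, and meets 1:64 | certainly below 64 |
| polio `<=8` | 8 | seropositive | may be below 8 |
| RV IgA `<20` | 10 | negative | negative |
| RV IgA `<40` | 40 | meets 20 U/mL | may be below 20 |
| RV IgA `<100` | 100 | meets 20 and 90 U/mL | may be below either |

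**Baseline, polio.** Baseline to Visit 7 is 30 + 30 + 30 = 90 days in Co-administration and 15 + 30 + 30 + 30 = 105 days in Staggered. The decay factor is 2^(-90/28) = 0.1077 or 2^(-105/28) = 0.0743. The 4-fold target is 4 × coded baseline × factor:

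- `<64` coded 64: 256 × 0.1077 = 27.6, or 256 × 0.0743 = 19.0. A seronegative infant needs only 8, so seroconversion becomes harder.
- `<16` coded 16: 6.9 or 4.8. A post-dose negative (coded 4) still fails and a titer of 8 still passes, so nothing changes at this timing.

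**Baseline, RV IgA.** `<40` coded 40 makes the infant not initially seronegative and triggers code 2020. That code also covers unknown status, so recoding alone would not restore the infant to the PPS; a retest below 20 U/mL would.

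**Borderline primary result (polio 2).** Expected non-converters per group: 160 × (1 - 0.9383) = 9.9. One infant is 1/160 = 0.625 points. With Staggered at 150/160, the lower limit is:

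- Co-administration 143/160: -10.86% (fail)
- 144/160: -10.14% (fail)
- 145/160: -9.41% (pass)

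**Type I error at the margin (83.83% against 93.83%).** The recoded share is my assumption: true non-converters scored as converted, as a percentage of all samples in the group.

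| Share | Co-administration only | Same share in both |
|---|---|---|
| 0% | 2.4% | 2.4% |
| 0.5% | 3.3% | 2.4% |
| 1% | 4.5% | 2.4% |
| 2% | 8.1% | 2.3% |
| 5% | 32.9% | 1.9% |

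One refinement: if the rule caught the same fraction g of non-converters in each group, the shares would differ slightly, because at the margin Co-administration has more non-converters (16.17% against 6.17%). The difference becomes -10 × (1 - g). At g = 3% it is -9.7 points, and the same enumeration gives an error of 2.9%.

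**GMT.** If the true titer is below 8, `<16` coded 16 instead of 4 overstates that infant 16/4 = 4-fold, and `<64` coded 64 overstates it 64/4 = 16-fold. One such infant among 160 raises the group GMT by a factor of 4^(1/160) = 1.009 or 16^(1/160) = 1.017.

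**The case against.** The strongest reply is that the row may never be used. Polio serum is tested from 1:8, the seropositivity threshold itself, so an ordinary negative is `<8` and is coded correctly; `<16` would need testing to start higher. RV IgA is read from a standard curve, and nothing says that `<40` is ever reported. The list looks generic, since it also maps POS and NEG strings although both assays are quantitative. This stands as an argument about frequency. It does not make the rule right when triggered.

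A reader might infer more than the documents support:

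- **That small infant samples produce such results.** No document says that a short sample is tested from a higher dilution. At Visit 7 the serum serves only the polio assays (Protocol 8.1.3), so it is not shared with the ELISA.
- **That every error favours a positive.** This fails at baseline: polio `<64` raises the hurdle, and RV IgA `<40` removes the infant from the count.
- **That the rule biases the trial towards non-inferiority.** This needs a larger recoded share in Co-administration. Both groups have the same Visit 7 sample and assay, and the 144-to-145 example is a chosen borderline case.
- **That 6.2.9 contradicts 4.1.1 and 6.2.4.1.** Those sections concern missing or non-evaluable results. Without a definition of non-evaluable, a conflict is not established.

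The reply also shows that simply blanking such results is a poor repair: it would drop possible low responders from the denominator and could itself raise the rate.

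**Conclusion.** The point holds as a defect in a stated derivation rule. When a `<` result with a bound above the cut-off occurs, or a `<=` result at or above it, the SAP assigns a value that can be, and for `<64` against 1:64 certainly is, on the wrong side of the threshold. No other section corrects this.

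Its practical size is unknown. For polio it is probably rare or nil, given the 1:8 starting dilution; for RV IgA the documents allow no estimate. One infant moves a seroconversion rate by 0.625 points, which matters only near the margin. Type I error is not inflated when the recoded shares are equal, and stays near nominal (2.9%) if 3% of non-converters in each group were caught. It reaches 4.5% or 8.1% only under an assumed 1% or 2% recoding confined to Co-administration, for which the documents offer no mechanism. These figures assume cut-offs of 8 and 20 U/mL and 160 evaluable infants per group. The repair is justified because it is cheap and settles the handling in advance in an open-label trial, not because harm has been shown.

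**What to change.** Amend the two rows of SAP 6.2.9 (`< value` above the cut-off; `<= value` at or above it):

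- For threshold endpoints, use a censored result only where its bound decides the answer; `<64` is a no for 1:64.
- Score an undecided post-dose result as not meeting the threshold in the primary analysis, with a sensitivity analysis setting it to missing.
- Treat an undecided baseline status as unknown. For RV IgA, code 2020 still applies, but for the correct reason.
- Do not enter the upper bound as an exact value in GMT or GMC.
- Where serum remains, retest from the lowest dilution and use that result.

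The cost is two derivation rows, the matching code and one small sensitivity table; the sample size and primary method are unchanged. The downside is that a few results may be scored conservatively or become missing. If no such result occurs, no reported figure changes.
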